## 18. WORK PACKAGE 6: DEVELOPMENT OF ACTIONABLE TOOLS

---

In work package 6, we will co-produce a set of actionable tools based on the emerging findings and in co-production with the LEAG as well as representatives from commissioning and providers.

### 18.1. Dissemination and outputs

We have a multifaceted strategy to disseminate our research findings. We will produce outputs for each work package (co-produced with the LEAG and PPI). These will be available to download on our project specific website [www.mimosstudy.org.uk](http://www.mimosstudy.org.uk) . We will use social media to engage with a range of people in relation to our findings, such as Twitter (e.g. using Twitter chats). We will coordinate press releases from our respective institutions and organisations to maximise visibility of our findings, and we will publish in open access peer reviewed journals, and present our findings at relevant conferences. In terms of the survivor and third sector we will be able to work with [name] at the Survivors Trust and [name] at Survivor's Voices and use their networks to disseminate.

## 19. GENERIC CONSIDERATIONS ACROSS WORK PACKAGES

---

### 19.1. Data Management, Permissions and Contracts

A Data Management Plan has been developed [MiMoS\_238240\_Data Management Plan\_v1\_16.08.2019]. All data will be stored in accordance with GDPR and the Data Protection Act (2008) on University of Leeds, University College London and Kings College London approved cloud based storage with relevant encryption and access restrictions applied. Relevant Data Sharing/Collaboration/Confidentiality agreements will be in place between all University collaborators, transcribers, translators and analytic companies. Similarly, relevant management permissions will be sought from all non-NHS organizations that we will be advertising or recruiting through.

### 19.2. Provider & Commissioner Involvement

We have engaged with a range of providers and commissioners in the development of the proposal and we will convene a “programme steering group” which will include SARC commissioners, SARC Clinicians and Medical Directors, Public Health England regional commissioner(s).

### 19.3. Patient & Public Involvement (PPI)

The Survivor voice and perspective is very important to our research plans, and as such we intend to work in partnership with survivors for all aspects of the study. The lead coordinator of our involvement approach will be [name].

We convene a Lived Experience Advisory Group (LEAG). The LEAG will work closely with the researcher(s) on all aspects of the study – planning, data collection, and being part of the synthesis phase as well as the overall study analysis phase integrating data from all work packages. LEAG members can participate in a number of ways including face to face meetings, telephone calls, Skype and email. The research will also draw upon ‘Turning Pain into Power: A Charter for Organizations Engaging Abuse Survivors in Projects, Research & Service Development’. Similarly, [name] of Survivor’s Trust is part of the core research team, and [name] from Survivor’s Voices is a key contributor, and advisor, to the research.

#### **19.4. Ethical Considerations**

We will develop comprehensive Standard Operating Procedures (SOP) which outline in more detail how to manage ethical considerations such as those outlined briefly below (i.e. to assess and manage distress and risk/ data management etc). Researchers should ensure they are up-to-date on relevant training such as Good Clinical Practice (GCP) and specifically trained to work with survivors. Please speak to your WP Lead if you feel you are not up-to-date with relevant training.

#### **19.5. Assessment & Management of Risk**

We will have clear distress and risk management standard operating procedures (SOPs) to ensure that people are safe within the study, so that timely and appropriate help is received should issues of concern be identified. A senior clinically trained member of the research team will be “on call” by phone during all data collection periods.

While many people find talking about their experiences to be helpful, some people may find that completing the questionnaire / taking part in the interview brings up issues that cause emotional distress. In this case the researcher will provide immediate emotional support to the participant, offer to pause or postpone the data collection, and, if the participant asks, will contact a person of the participant’s choice (e.g. current care coordinator, carer, friend, family member, or colleague) for them.

If service users or carers report any untoward feedback, the researcher conducting the data collection / interview will confirm with the participant whether or not they would like the researcher to pass this on to the service or other relevant person. If the untoward feedback is of a nature that leads the researcher to be concerned for the safety of the participant or that of others, the participant will be informed that the feedback will be passed on to the relevant service or person to be addressed, but that if desired and possible they will remain anonymous.

In the event that the researcher feels concerned for their own safety they will be advised to bring the interview to an end. All face-to-face interviews will be conducted on NHS/SARC premises or other suitable spaces, and local safety policies and protocols should be adhered to by all researchers (e.g. informing local staff at the start of an interview, and again once the interview has been completed). All staff conducting research relating to the trial will be familiar with and have copies of the trial SOPs.

Please refer to the SOPs for more details

## 19.6. Recording & Reporting of Events & Incidents

### 19.6.1. Definitions of Adverse Events

Term	Definition
Adverse Event (AE)	Any untoward medical occurrence in a patient or study participant, which does not necessarily have a causal relationship with the procedure involved.
Serious Adverse Event (SAE).	Any adverse event that: 

• results in death,

• is life-threatening*,

• requires hospitalisation or prolongation of existing hospitalisation**,

• results in persistent or significant disability or incapacity, or

• consists of a congenital anomaly or birth defect

*A life- threatening event, this refers to an event in which the participant was at risk of death at the time of the event; it does not refer to an event which hypothetically might have caused death if it were more severe.
 
** Hospitalisation is defined as an in-patient admission, regardless of length of stay. Hospitalisation for pre-existing conditions, including elective procedures do not constitute an SAE.
	

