## **12. THE EFFECTIVENESS OF SEXUAL ASSAULT REFERRAL CENTRES WITH REGARD TO MENTAL HEALTH AND SUBSTANCE USE: A NATIONAL MIXED METHODS STUDY**

### **Mixed Methods Study of SARCs (MiMoS)**

#### **12.1. Background**

Sexual assault referral centres (SARCs) are a one-stop shop for the treatment of people who have experienced sexual assault. They bridge criminal justice and health services in recognition of the range of needs that are presented. This includes forensic medical examinations, physical and mental health checks, safeguarding and risk assessment, as well as psychosocial support. SARCs are also able to refer or signpost to other agencies in the local area should a need be identified. The HS&DR has commissioned this research to examine how SARCs are responding to the mental health and substance use needs of its service users.

Mental ill health is common in people who attend SARCs. In Holland (Bicanic et al., 2014), the United States (Brown et al., 2013), and England (Brooker and Durmaz, 2015), approximately 40% of SARCs attendees have been estimated to have a mental health problem. In a recent audit of Thames Valley SARCs, Brooker et al (under review) found: that 69% of attendees could be defined as experiencing a mental health problem; 20% had a history of admission to a psychiatric unit; 32% were drinking at 'hazardous' levels; and 45% had previously self-harmed. In a secondary analysis of data from the Adult Psychiatric Morbidity Survey, Brooker and Tocque (2016) found that there was a consistent relationship between risk of mental health and substance use problems and the level of sexual violence experienced. They concluded that having mental health expertise in SARCs was crucial. However, the National Service Specification for SARCs (NHS England, 2015) whilst acknowledging mental health issues are common, states only that SARCs should ensure the provision of appropriate psychosocial support according to need, and where this exceeds what Increasing Access to Psychological Therapies (IAPT) can support, then they will be referred to secondary mental health services.

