#### 19.6.4. Procedures for recording and reporting Serious Adverse Events

All adverse events will be recorded in the study AE form, and the sponsor's AE log.

All SAEs must be recorded on a serious adverse event (SAE) form. The CI/Work Package Lead or designated individual will complete an SAE form and the form will be preferably emailed to the Sponsor within 1 working day of becoming aware of the event. The CI or WP Lead will respond to any SAE queries raised by the sponsor as soon as possible.

[figure not shown]
Where the event is unexpected and thought to be related to the procedure this must be reported by the Investigator to the Health Research Authority and REC within 15 days of research team awareness of the event. You will find information on SAE reporting to the REC on the HRA website, <https://www.hra.nhs.uk/approvals-amendments/managing-your-approval/safety-reporting/>.

Completed forms for unexpected SAES must be sent within 1 working day of becoming aware of the event to the Sponsor

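### The SAE definition is a closed five-item list with no limb for other medically important events, so self-harm or a suicide attempt that is not admitted, not life-threatening and not disabling is never an SAE, even if the study caused it

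*Protocol*

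**What the plan says.** Section 19.6.1 of the protocol defines a serious adverse event as one that meets any of five conditions. It "results in death"; it "is life-threatening"; it "requires hospitalisation or prolongation of existing hospitalisation"; it leaves disability or incapacity that is persistent or significant; or it is a congenital anomaly or birth defect. The word 'or' stands before the last item, and no general item follows.

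Footnotes narrow two of the five. On threat to life: "this refers to an event in which the participant was at risk of death at the time of the event", and "it does not refer to an event which hypothetically might have caused death if it were more severe". On hospitalisation: "Hospitalisation is defined as an in-patient admission, regardless of length of stay".

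Section 19.6.4 sets the consequences. Every adverse event goes on the study AE form and the sponsor's AE log. For the serious ones, "All SAEs must be recorded on a serious adverse event (SAE) form", and that form is to reach the sponsor within one working day. A further sentence requires a report to the HRA and REC within 15 days where the event is unexpected and thought to be related.

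Section 12.1 describes the population through a recent audit of Thames Valley SARCs, in which "45% had previously self-harmed".

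**The concern.** An SAE definition decides which harms are notified quickly and which are only logged. In a questionnaire and interview study of people who have recently attended a SARC, self-harm is a foreseeable serious harm of taking part. Many such episodes could be treated in an emergency department or in the community without admission. The present list is built around death, admission and lasting damage, and it includes congenital anomaly. It has no place for an event that matters clinically but meets none of those conditions.

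At stake is prompt notice. A self-harm episode that the researcher attributes to the interview could be logged with no stated deadline for telling the sponsor, and possibly with no report to the REC. A signal that the procedures were causing harm would then arrive later than the protocol's own deadlines intend.

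**Working it through.** The protocol gives no figure to reproduce. The check applies the definition to four cases and then looks for another rule that would catch the one left out.

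**Step 1: apply the five limbs of 19.6.1 to self-harm or a suicide attempt.**

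| Case | Limb met | SAE? |
|---|---|---|
| (a) Not admitted, no actual risk of death, no persistent or significant disability or incapacity | None | No |
| (b) Not admitted, but at risk of death at the time | Life-threatening | Yes |
| (c) Not admitted, but leaves persistent or significant disability or incapacity | Disability or incapacity | Yes |
| (d) Admitted as an in-patient, for any length of stay | Hospitalisation (unless the footnote on pre-existing conditions is applied) | Yes |

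The gap is case (a) alone. The footnote on pre-existing conditions plays no part in it, because case (a) involves no admission.

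**Step 2: does relatedness or severity bring case (a) back in?** No. Causality is not part of the definition, and severity in 19.6.2 is a separate scale. An event can hold the highest grade on both scales, clearly damaging to health and definitely related, and still fail all five limbs.

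**Step 3: is there another test of seriousness?** Section 19.6.2 says each event will be assessed for severity, causality, seriousness and expectedness as set out below it. Severity, causality and expectedness are then defined; seriousness is not. The list in 19.6.1 is therefore the only test. The SOPs named in 19.4 and 19.5 deal with ethics, distress and risk. They are not shown, and the SAE definition does not refer to them.

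**Step 4: what does case (a) lose under 19.6.4?**

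- AE form and sponsor's AE log: kept, since they apply to all adverse events.
- SAE form and its one-working-day deadline: lost, since they apply to SAEs only.
- 15-day report to the HRA and REC: depends on the reading. The sentence speaks of an event without the word serious, but it stands under the heading on SAE procedures, and the text after it concerns forms for unexpected SAEs. The SAE reading is the more natural one; it is not certain.

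**Step 5: would related self-harm count as unexpected?** Probably. Expectedness is judged against what the protocol says about the procedure, and 19.5 names emotional distress as the possible effect of taking part, not self-harm. Case (a), if related, would then have the combination that the 15-day rule is meant to catch.

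**Step 6: size.** If the audit proportion held in the WP3 sample of 360, 0.45 × 360 = 162 participants would have a history of self-harm. That figure is past history, not incidence during follow-up. The protocol gives no incidence, no proportion treated without admission and no proportion related, so the number of case (a) events cannot be derived from it.

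**The case against.** Four objections deserve an answer.

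First, a reader might infer that any self-harm or suicide attempt treated without admission falls outside the SAE definition. The text does not support that. The life-threatening limb and the disability limb need no admission, and the latter covers significant incapacity as well as persistent. Cases (b) and (c) are SAEs wherever they are treated. The point is confined to case (a).

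Second, a reader might infer that such events go unseen. They do not. All adverse events are recorded and graded, the Independent Oversight Group (section 8) reviews safety data, a senior clinically trained team member is on call during data collection (19.5), and urgent safety measures must be notified to the REC and sponsor within three days. All of this stands and limits the practical loss. None of it supplies the missing limb or a deadline for case (a).

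Third, the 15-day rule may already reach beyond SAEs, because it speaks only of an event. A figure just before that sentence and the SAE flow chart are not visible in the text available for review. This stands as an uncertainty: loss of the REC report can be claimed only conditionally.

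Fourth, no statement in the protocol is false or self-contradictory; this is a design choice in a questionnaire, interview and records study. That is fair, and it bears on how serious the point is. It is still a stated rule that gives a worse safety result than an easily available alternative.

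**Conclusion.** The point holds in its narrow form. Self-harm or a suicide attempt that is treated without in-patient admission, carries no actual risk of death at the time and causes no persistent or significant disability or incapacity is not an SAE under 19.6.1, whatever its cause or severity grade. The certain loss is the SAE form and the one-working-day notice to the sponsor. The loss of the 15-day HRA and REC report rests on reading that rule as limited to SAEs, which its position favours but does not settle.

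No event count should be attached. The 45% figure shows why the gap matters in this population but is not a rate during the study. The team can also act only on events it learns of, and WP3 collects data at baseline and six months. The conclusion does not depend on any assumed rate, nor on the content of the unseen SOPs unless they change the SAE definition. This is a worthwhile, inexpensive improvement rather than a fault that undermines the study.

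**What to change.** Add a sixth limb to the list in 19.6.1: or is otherwise judged medically important by the investigator. Add a note that self-harm and suicide attempts without in-patient admission must be considered under this limb. The note should require consideration, not automatic classification, so that minor episodes do not all become SAEs and the investigator's judgement is kept. Leave the reporting routes in 19.6.4 as they are; events that meet the new limb then follow them, and the doubt about the scope of the 15-day rule no longer matters for those events.

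The cost is a line and a note in the protocol, with matching changes to the AE form and the SOP. The downside is somewhat more SAE forms, mostly for events unrelated to the study, which need no report to the REC.

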### 19.6.2. Assessments of Adverse Events

Each adverse event will be assessed for severity, causality, seriousness and expectedness as described below.

### Severity

Category	Definition
Mild	The adverse event does not interfere with the participant's daily routine, and does not require further procedure; it causes slight discomfort
Moderate	The adverse event interferes with some aspects of the participant's routine, or requires further procedure, but is not damaging to health; it causes moderate discomfort
Severe	The adverse event results in alteration, discomfort or disability which is clearly damaging to health

### Causality

The assessment of relationship of adverse events to the procedure is a clinical decision based on all available information at the time of the completion of the case report form.

The differentiated causality assessments will be captured in the AE Log and SAE form.

The following categories will be used to define the causality of the adverse event:

Category	Definition
Definitely:	There is clear evidence to suggest a causal relationship, and other possible contributing factors can be ruled out.
Probably:	There is evidence to suggest a causal relationship, and the influence of other factors is unlikely

Possibly	There is some evidence to suggest a causal relationship (e.g. the event occurred within a reasonable time after administration of the study procedure). However, the influence of other factors may have contributed to the event (e.g. the participant's clinical condition, other concomitant events).
Unlikely	There is little evidence to suggest there is a causal relationship (e.g. the event did not occur within a reasonable time after administration of the study procedure). There is another reasonable explanation for the event (e.g. the participant's clinical condition).
Not related	There is no evidence of any causal relationship.
Not Assessable	Unable to assess on information available.

### *Expectedness*

Category	Definition
Expected	An adverse event which is consistent with the information about the procedure listed in this protocol.
Unexpected	An adverse event which is not consistent with the information about the procedure listed in this protocol.

### 19.6.3. Recording adverse events

All adverse events will be securely documented by the researcher.

#### 19.6.4. Procedures for recording and reporting Serious Adverse Events

All adverse events will be recorded in the study AE form, and the sponsor's AE log.

All SAEs must be recorded on a serious adverse event (SAE) form. The CI/Work Package Lead or designated individual will complete an SAE form and the form will be preferably emailed to the Sponsor within 1 working day of becoming aware of the event. The CI or WP Lead will respond to any SAE queries raised by the sponsor as soon as possible.

[figure not shown]
Where the event is unexpected and thought to be related to the procedure this must be reported by the Investigator to the Health Research Authority and REC within 15 days of research team awareness of the event. You will find information on SAE reporting to the REC on the HRA website, <https://www.hra.nhs.uk/approvals-amendments/managing-your-approval/safety-reporting/>.

Completed forms for unexpected SAES must be sent within 1 working day of becoming aware of the event to the Sponsor

**Email forms to: [[contact]](mailto:[contact])**

Flow Chart for SAE reporting (this simple flow chart is for single site study, please amend in line with study specific requirements)

#### **19.6. Reporting Urgent Safety Measures**

If any urgent safety measures are taken the CI/ PI shall immediately and in any event no later than 3 days from the date the measures are taken, give written notice to the relevant REC and Sponsor of the measures taken and the circumstances giving rise to those measures.

#### **19.7. Protocol deviations and notification of protocol violations**

A deviation is usually an unintended departure from the expected conduct of the study protocol/SOPs, which does not need to be reported to the sponsor. The CI will monitor protocol deviations.

A protocol violation is a breach which is likely to effect to a significant degree –

- (a) the safety or physical or mental integrity of the participants of the study; or
- (b) the scientific value of the study.

The CI and sponsor will be notified immediately of any case where the above definition applies during the study conduct phase.

#### **19.8. Monitoring and Auditing**

The Chief Investigator will ensure there are adequate quality and number of monitoring activities conducted by the study team. This will include adherence to the protocol, procedures for consenting and ensure adequate data quality.

The Chief Investigator will inform the sponsor should they have concerns which have arisen from monitoring activities, and/or if there are problems with oversight/monitoring procedures.

#### **19.9. Peer and Regulatory Review**

The Sponsor considers the procedure for obtaining funding from the NIHR to be of sufficient rigor and independence to be considered an adequate peer review.

#### **19.10. Funding and Supply of Equipment**

The study funding has been reviewed by the UoL Research Office, and deemed sufficient to cover the requirements of the study. NHS costs will be supported via the Local Clinical Research Network.

The research costs for the study have been supported by the NIHR HS&DR programme grant 16/117/03.

**19.11. Training**

The Chief Investigator will review and provide assurances of the training and experience of all staff working on this study. Appropriate training records will be maintained in the study files.

